According to annual statistics, the sepsis cost 5.2% in 2011 medical cost in the United States. Total \$20 billions were cost for treatment of sepsis and its related medical conditions.¹ In Taiwan, the medical expenditure of patients in the medical intensive care units also is very huge. The peripheral artery disease (PAD) is also prevalent in the elderly and in most situations under-diagnosed. In Taiwan, an accurate data on PAD prevalence is absent. According to the screening program in National Taiwan University Hospital Hsinchu branch, the prevalence of PAD among patients receiving hemodialysis is high (48–30%). Many patients do not receive screening and adequate care.

Peripheral artery disease- its impact on the outcomes

Patients with PAD have four-fold increase in the risk of myocardial infarction and three-fold increase in the risk of stroke.^{2,3}

Medications for treatment of PAD

LEAD (lower extremity artery disease) is a subset of PAD. To date, there is no specific trial addressing the role of antiplatelet agents in the full spectrum of LEAD, including asymptomatic, intermittent claudication, and critical lower limb ischemia.

COMPASS ⁴	Rivaroxaban 5 mg bid Rivaroxaban 2.5 mg bid with aspirin Aspirin	Total 27402 patients with CAD or LEAD	To be reported
CAPRIE ²	Clopidogrel Aspirin		Not focused on PAD
CASPAR ⁵ CHARISMA ⁶	Clopidogrel plus aspirin Aspirin mono-therapy		Not focused on PAD
Fowkes, 2010 ⁷	Aspirin for subclinical LEAD	Asymptomatic LEAD with ABI < 0.95	No benefit
Belch, 2008 ⁸	Aspirin for subclinical diabetic LEAD	Asymptomatic LEAD in diabetic with ABI < 1.0	No benefit
Antithrombotic collaborative ⁹	Aspirin for prevention of MACE	Symptomatic LEAD	Benefit

Clinical needs

There are guidelines for treatment of sepsis and PAD. The diagnosis, treatment, and outcomes are well defined for sepsis and PAD, respectively. However, there is no consensus on the benefit of screening of PAD in patients presented with sepsis. The current diagnosis and treatment are clinically driven by patient's new change in limb physical examinations. Usually, we initiate the work-up for PAD after toe cyanosis or frank gangrene occurs.

4. Previous studies focusing on PAD in sepsis patients

There is a lack of dedicated research of PAD among patients presented with sepsis. With the search term “peripheral artery disease” and “critical care”, there is only one article on PAD and chronic obstructive pulmonary disease”.¹⁰

5. Goals of project

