Purpose (for clinicaltrials.gov registration)

- Study type: interventional
- Study Design:
 - Allocation: randomized - Endpoint classification: efficacy study - Intervention model: parallel - Masking: single blind (outcomes assessor) - Primary purpose: treatment
- Official title: as the study project title

Objectives

1. Perform a screening for PAD among patients admitted to the medical intensive care units and meet the sepsis diagnosis criteria (quick SOFA score ≥ 2 points).
2. Follow the outcomes (all cause mortality at 30 days, stroke, myocardial infarction, lower limb ischemia requiring amputation) of patients who have evidence of ABI < 0.9 or PAD by additional vascular Duplex confirmation.
3. To evaluate the prevalence of PAD among patients admitted to our intensive care units.
4. To obtain the diagnosis of PAD early on the admission day among multiple care teams (cardiologists, chest physicians, and critical care specialist) and to give adequate medical treatment as needed (anti-platelet agents).
5. To evaluate whether early diagnosis of PAD in sepsis patients will lead to decision-makings that will influence the patient's survival.
6. To evaluate whether early diagnosis of PAD will lead to decreased complications rate of invasive arterial line monitoring.

6. Methods and procedures

Research design

1. Research design: prospective cohort study
2. Locations: the medical intensive care units (MICU) of National Taiwan University Hospital, Hsinchu Branch.
Patient population: sepsis patients who meet the quick SOFA score ≥ 2 points.
3. The investigator is responsible of this research: [name].
4. Study parameters:
 1. The prevalence of PAD among patients admitted to the MICU with sepsis
 2. The outcomes of PAD patients presented with sepsis to the MICU
5. Research field: critical care medicine, cardiovascular disease, peripheral artery disease
6. Keywords: peripheral artery disease, sepsis
7. Study design: observational study (cohort study)
 1. Collection of data: prospective
 2. Inter rim analysis: yes
 3. Investigator manual: yes

2. Study population

1. Patient number: 200 patients
2. Age limitation: 20-100 years old
3. Inclusion criteria:
 1. Admission diagnosis with sepsis, meeting quick SOFA criteria ≥ 2 points (respiratory rate $\geq 22/\text{min}$, altered mentation, systolic blood pressure $\leq 100 \text{ mmHg}$, each item is one point)
 2. Within the study age limitation
 3. Willing to participate the study
4. Exclusion criteria:

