1. This research will not require a paper inform consent. Because this study has minimal risk for the study participant- the ABI study was non-invasive. And this study will be carried in the medical intensive care units, it is focused on emergency medicine. The patients with sepsis admitted to the MICU usually are already in a critical condition and there is a need to aggressively diagnose any disease that will lead to poor outcomes. The benefits of diagnosing a PAD early outweigh the risk carried by the study method.

6. The study method

1. After enrollment, within 24 hours: the nurse will measure the ankle-brachial index (ABI). The measurements are to be done by A-line at any arteries that physician considered appropriate and additional bilateral lower limb blood pressure measurements. A Doppler scanner is allowed to be used to facilitate the measurement of ABI.
2. The definition of ABI (ankle-brachial index): the leg systolic blood pressure divided by the higher readings of bilateral brachial artery. If ABI < 0.9, a diagnosis of PAD is made.

7. The follow-up

1. At the time of admission: APACHE score
2. The treatment patient received: ventilator, vasopressor, inotropic agent, blood pressure, and the diagnosis.
3. Patient will be followed at 7 days, 30 days, and 90 days.
4. Medications will be recorded, especially: aspirin (Bokey), cilostazol (Pletal), clopidogrel (Plavix), statin.
5. Clinical events will be documented:
 1. Mortality
 2. Acute myocardial infarction
 3. Stroke, ischemic
 4. Limb gangrene resulting in amputation

8. Statistical method

1. We plan to enroll 200 patients. Patients will be grouped into patients with PAOD and patients without PAOD. We then compare them in the following parameters: clinical data, laboratory data, survival and other outcome data. Two-sample student's t tests will be used for the comparisons of continuous variables. Chi-square test will be used to detect difference between categorical variables. Difference is considered statistically significant if $P < 0.05$. All statistics works were analyzed using the SPSS 17.0 software (Chicago, IL, USA), R software (Gimc packages).

7. Anticipated results

1. Evaluate the care process and quality in patients in the MICU
2. Evaluate the prevalence of PAD in patients with sepsis admitted to the MICU
3. Investigate the influence of PAD to the outcomes of sepsis

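### The limb outcome does not have to be new after enrolment, and limb tissue status at entry is not a specified data item, so amputations for gangrene already present at admission would count as follow-up events

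*Combined protocol and SAP*

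**What the plan says.** All places are in the combined protocol and SAP.

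- **Eligibility** (section 6, Study population, items 3 and 4). Entry needs sepsis with a quick SOFA score of at least 2, age 20 to 100, and willingness to take part. The exclusions cover refusal, a list of vulnerable or terminal groups, and cancer under treatment. Gangrene, foot infection, previously diagnosed PAD, revascularisation and earlier amputation are not mentioned.
- **Data at or near entry** (section 6, The study method and The follow-up). The plan lists an APACHE score at admission, ABI with bilateral leg pressures within 24 hours, treatments, blood pressure, an unspecified diagnosis, and medications.
- **Limb event** (section 6, The follow-up, item 5): "Limb gangrene resulting in amputation". Objective 2 in section 5 describes the limb outcome as ischaemia leading to amputation. Neither wording refers to lesions arising after enrolment.
- **Analysis** (section 6, Statistical method): "We plan to enroll 200 patients"; "Patients will be grouped into patients with PAOD and patients without PAOD"; "Chi-square test will be used to detect difference between categorical variables". The significance threshold is 0.05. No adjustment is described.
- **Purpose.** Section 3, Clinical needs, says of current practice: "Usually, we initiate the work-up for PAD after toe cyanosis or frank gangrene occurs". Objective 5 begins "To evaluate whether early diagnosis of PAD in sepsis patients will lead to decision-makings", and section 7, item 3, is "Investigate the influence of PAD to the outcomes of sepsis".

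**The concern.** A follow-up outcome should be something that can still happen to the patient after entry. Take a patient whose sepsis arises from an infected gangrenous foot. Nothing in the criteria keeps that patient out. If the ABI is below 0.9, the patient joins the PAD group, and a later amputation of that foot meets the event definition. The lesion was there on arrival, so the event says nothing about what PAD did during or after the septic episode. It also cannot bear on earlier diagnosis, because this patient is already at the stage where Clinical needs says work-up usually begins.

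If these cases sit mainly in one group, the error does not average out. It raises the amputation rate in the PAD group, and a reader would take the difference as the influence of PAD on the outcome of sepsis. Since the specified data contain no limb tissue status at entry, the cases could not reliably be separated afterwards.

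**Working it through.** **1. The plan's own figures.** The sample size of 200 comes with no power, effect size, event rate or precision target, so there is nothing to reproduce, and this point does not dispute it. No frequency of gangrene or amputation is given. The only PAD rate is 30% to 48%, in the hospital's haemodialysis patients (section 3); it serves below only as an illustrative range for the group sizes.

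**2. Reading the rules together.**

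| Step | Rule | Effect on a patient with gangrene at entry |
|---|---|---|
| Eligibility | No limb or PAD-history condition | May be enrolled |
| Classification | ABI below 0.9 | PAD group, if the ABI is low |
| Entry data | No limb tissue item specified | Lesion not flagged |
| Event | Gangrene leading to amputation, not limited to new lesions | Counted |
| Analysis | Unadjusted chi-square | Enters the PAD rate in full |

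**3. Sensitivity of the planned test.** With a and b the patients with and without amputation in the PAD group, c and d the same in the other group, and N = 200, the uncorrected statistic is N(ad − bc)² / [(a+b)(c+d)(a+c)(b+d)].

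Assume 30% PAD: 200 × 0.30 = 60 v 140. Assume two truly new amputations in each group.

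- No cases present at entry, 2/60 v 2/140: 200 × (2×138 − 58×2)² / (60×140×4×196) = 5,120,000 / 6,585,600 = 0.78, p = 0.38.
- Two added to PAD, 4/60 v 2/140: 200 × (4×138 − 56×2)² / (60×140×6×194) = 38,720,000 / 9,777,600 = 3.96, p = 0.047. The risk ratio moves from 2.33 to 4.67.
- Four added, 6/60 v 2/140: 200 × (6×138 − 54×2)² / (60×140×8×192) = 103,680,000 / 12,902,400 = 8.04, p = 0.005, risk ratio 7.0.

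Assume 48% PAD: 96 v 104, again two new amputations in each group.

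- 2/96 v 2/104: p = 0.94, risk ratio 1.08.
- Four added, 6/96 v 2/104: p = 0.12.
- Six added, 8/96 v 2/104: p = 0.038, risk ratio 4.33.

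**4. Dependence on the test.** The plan does not say whether the chi-square is continuity-corrected. For 4/60 v 2/140 the corrected value is 200 × (440 − 100)² / 9,777,600 = 2.36, p = 0.12, and Fisher's exact p is 0.068. The expected PAD-group count there is 6 × 60/200 = 1.8, too small for the uncorrected p to be trusted. With four added, Fisher's p is 0.010. For 8/96 v 2/104 it is 0.051.

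**5. Known and newly detected PAD.** With total prevalence p and share f already known, detection among patients without known PAD is p(1 − f)/(1 − pf). Assume p = 0.30 and f = 0.25: of 60 PAD patients 15 are known and 45 new, so 45/185 = 24.3%, against a total prevalence of 30%. For f from 10% to 50% the figure is 27.8% to 17.6% at p = 0.30, and 45.4% to 31.6% at p = 0.48. The total stays valid; it answers a different question from new detection.

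**The case against.** The strongest reply is that the protocol does measure the limbs at baseline. ABI with leg pressures is taken within 24 hours, and a diagnosis and medications are recorded. An investigator manual is said to exist and the data sit in REDCap; neither the manual nor the data-entry form is among the documents. This stands against the inference that no baseline limb status is collected. The text supports only that tissue status and PAD history are not specified. An ABI is a pressure ratio and does not show whether gangrene was present, and no rule links any entry finding to the event definition.

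Three further readings are tempting and not supported.

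- *Known PAD spoils the prevalence figure.* It belongs there: the study parameter is PAD prevalence among septic MICU patients, and no endpoint for screening yield or new detection is defined. Splitting known from new is an addition that serves the early-diagnosis objectives, not a correction of a miscounted endpoint.
- *This is reverse causation.* In the foot-infection example, limb disease precedes both the sepsis and the amputation. The fault is one of timing: a condition present at entry is counted as a new event.
- *A false limb finding is likely.* The documents do not say how many such patients would be enrolled or which ABI group they would fall in. Scenarios with no new amputations at all look starker than they should. For example, 3/60 v 0/140 gives Fisher p = 0.026, but one amputation in the other group (3/60 v 1/140) moves it to 0.082, with an uncorrected chi-square p of 0.047.

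It is also fair that amputation is one of four listed events, so the reach is narrow.

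**Conclusion.** The point holds for the limb outcome. As written, the event definition admits amputations for lesions present at entry, and the specified data would not identify them. Mortality, stroke, myocardial infarction and total PAD prevalence are not affected by this definition.

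The direction of bias, towards a higher rate in the PAD group, rests on the assumption that gangrene at entry goes mainly with an ABI below 0.9. That is plausible, but not stated in the documents. The size is unknown. Under the assumed counts, two to six cases among 200 patients move the uncorrected chi-square from clearly non-significant to below 0.05; at the lower end of that range Fisher's test does not follow. The figures show how fragile a comparison with very few events is, and they do not estimate the bias in this study. The change should be made, but the rest of the study does not depend on it.

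**What to change.** 1. **Record at admission**, from chart and bedside examination and for each limb: gangrene, toe cyanosis, and foot infection as the source of sepsis. Also record any previously diagnosed PAD, revascularisation or amputation.
2. **Redefine the limb event** in The follow-up, item 5: an amputation counts only when that limb was free of gangrene at entry. Working by limb keeps a genuine new event in the other leg. List the remaining amputations separately by group.
3. **Keep total PAD prevalence as planned**, and add its split into known and newly detected PAD. Base statements on early diagnosis (objectives 4 and 5) on the newly detected group.

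The cost is a few REDCap fields that use information available at admission, and a sentence in the outcome definition. Eligibility and sample size stay as they are. There will be fewer limb events, so the limb comparison will be less precise, and the newly detected figure will be smaller than total prevalence wherever some PAD was already known. Limb status at entry may be hard to reconstruct later, so it should be collected prospectively.

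### Survival is compared by PAD status with t and chi-square tests only, is not defined as a time or a fixed-day status, and has no method for patients lost before day 90

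*Combined protocol and SAP*

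**What the plan says.** All places are in the combined protocol and SAP. In section 6, item 8 (Statistical method), the sample and groups are set out: "We plan to enroll 200 patients" and "Patients will be grouped into patients with PAOD and patients without PAOD". The comparison follows: "We then compare them in the following parameters: clinical data, laboratory data, survival and other outcome data". Two tests are named: "Two-sample student's t tests will be used for the comparisons of continuous variables" and "Chi-square test will be used to detect difference between categorical variables". Significance is judged at 0.05.

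Section 6, item 7 (The follow-up) gives every patient the same schedule: "Patient will be followed at 7 days, 30 days, and 90 days". It lists mortality as the first clinical event to document, but asks for neither an event date nor a date last known alive. The study population item sets follow-up at 3 months. Objective 2 in section 5 names all-cause mortality at 30 days, the only mortality outcome with a stated time point. The patient information security item lets patients withdraw at any time and has their data removed on request.

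No time-to-event method, censoring rule or rule for a missing outcome appears anywhere.

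**The concern.** Survival must be classed as continuous or categorical before either named test can be applied, and the plan does not class it.

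- If it is a time, the rule for continuous variables sends it to the t test, which treats the last contact day of a living patient as if it were a day of death.
- If it is a status at day 90, chi-square applies, but a patient lost earlier must be dropped or counted as alive. Nothing says which, so the choice would be made with the data in view.

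Mortality is the first outcome listed, and the effect of PAD on sepsis outcomes is an anticipated result in section 7. Some loss is foreseeable, since these are intensive-care patients followed to day 90 with free withdrawal and no described tracing of vital status. The plan also sets a P-value threshold without asking for an effect size or confidence interval.

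**Working it through.** **Inputs from the documents.** 200 patients; two groups by PAD status; t and chi-square tests at 0.05; contacts at days 7, 30 and 90. There is no plan figure to reproduce on this point: no event rate, loss rate or PAD share in sepsis is stated.

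**Assumptions.** 60 patients with PAD and 140 without (30% of 200; the only prevalence given is 30% to 48%, in haemodialysis patients). Exponential survival. A proportion l of each group has a loss time spread evenly over days 14 to 90, unrelated to prognosis.

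**Formulas.** For 90-day mortality p, λ = −ln(1 − p)/90. A patient with a loss time is still alive at it with average probability s = (e^(−14λ) − e^(−90λ))/(76λ). Observed deaths are D = (1 − l)p + l(1 − s), and the proportion lost is l·s. Mortality is D if the lost count as alive, and D/(1 − l·s) if they are dropped.

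**Step 1: 90-day status, true mortality 40% v 30%, loss 5% v 25%.**

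| | PAD | No PAD | Difference (points) |
|---|---|---|---|
| λ | 0.00568 | 0.00396 | |
| s | 0.7502 | 0.8169 | |
| Lost counted alive | 0.95×0.40 + 0.05×0.2498 = 0.3925 | 0.75×0.30 + 0.25×0.1832 = 0.2708 | 12.2 |
| Lost dropped | 0.3925/(1 − 0.0375) = 0.4078 | 0.2708/(1 − 0.2042) = 0.3403 | 6.8 |

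Independent simulations gave 12.0 to 12.2 and 6.6 to 6.8 for these, and 9.8 to 10.1 by Kaplan-Meier, against a true 10. The chance of a significant result was 40% with the lost counted alive, 13% with them dropped, 28% by log-rank and 5% by t test. The unstated coding rule alone moves it from 13% to 40%.

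**Step 2: 30-day status, same assumptions.** True mortality is 1 − 0.6^(1/3) = 0.1566 and 1 − 0.7^(1/3) = 0.1121, a difference of 4.4 points. With the calculation cut off at day 30, s becomes s30 = (e^(−14λ) − e^(−30λ))/(76λ), which is 0.1859 and 0.1930. The term 1 − s becomes 1 − s30 − (60/76)e^(−30λ), which is 0.1483 and 0.1060.
- Counted alive: 0.1562 − 0.1106, or 4.6 points.
- Dropped: 0.1562/0.9907 − 0.1106/0.9518, or 4.1 points.

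**Step 3: t test on recorded time, no true difference (35% in both groups).** Here λ = 0.00479. Mean time to death or day 90 is 0.35/λ = 73.1 days; for a patient with a loss time it is (1 − s)/λ = 45.1 days. At 5% v 25% loss the group means are 0.95×73.1 + 0.05×45.1 = 71.7 and 0.75×73.1 + 0.25×45.1 = 66.1 days, a gap produced by loss alone. Simulated rejection at a nominal 5%:

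| Loss, PAD v no PAD | t test | Chi-square, dropped | Chi-square, alive | Log-rank |
|---|---|---|---|---|
| 5% v 25% | 22–25% | 7.3–7.6% | 6.6–6.8% | 4.9–5.1% |
| 5% v 35% | 47% | 11% | 9% | 5% |

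**Step 4: no loss or equal loss.** With no loss, every method holds about 5%. With 10% loss in both groups and truth 40% v 30%:
- Counted alive: 0.3850 − 0.2883, or 9.7 points.
- Dropped: 0.3850/0.9250 − 0.2883/0.9183, or 10.2 points.

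**Step 5: a second set of assumptions.** PAD share 30% or 48%, mortality 30% or 50% in both groups, loss from day 7.
- At 30% v 10% loss, in either direction, chi-square was off by 2.3 to 4.6 points (counted alive), or by 3.0 to 4.2 points the other way (dropped), with rejection of 5.5% to 8.7%. Kaplan-Meier was within 0.5 point and log-rank rejected 3.5% to 5.5%.
- With a hazard ratio of 1.6 (PAD share 30%, no-PAD mortality 40%), a true 15.8 points became 11.1 or 20.2 at 30% v 10% loss, against 16.0 by Kaplan-Meier.
- In that same case with equal 20% loss, the estimates were 14.3 (alive), 15.6 (dropped) and 15.4 (Kaplan-Meier).

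**The case against.** The strongest defence is that mortality is listed beside infarction, stroke and amputation as a clinical event, that the schedule is the same for all, and that the one dated mortality outcome is at 30 days. Read that way, survival is a fixed-day status and chi-square is a suitable test. This largely stands for day 30, where step 2 shows a shift of no more than 0.3 point. It also means the t-test figures apply only if survival is analysed as a time, which the plan leaves open but does not state.

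A reader might infer three stronger claims that the documents do not support.

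- *The named tests cannot handle patients alive at day 90.* Under chi-square on 90-day status such a patient is simply a non-event. With complete follow-up its bias was about 0, and its power was 55% against 59% for log-rank in the hazard-ratio 1.6 case.
- *Follow-up will be unequal, so the contrast is biased.* No loss rate or difference in loss is stated. That PAD patients might be followed more closely because cardiologists are involved is a plausible inference, but the plan does not say so.
- *Censoring cannot be handled afterwards.* The protocol does not require dates, but that does not show that they go unrecorded in the database or hospital records.

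The time-to-event remedy also has a limit: Kaplan-Meier, log-rank and Cox methods remove the bias only if loss is unrelated to prognosis.

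What remains is that survival is undefined, follow-up runs to day 90, and no rule covers a patient lost before then.

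**Conclusion.** The point holds in a conditional form and should be fixed. The plan names two tests for an outcome it does not define and has no method for incomplete follow-up. The size depends on loss rates that the documents do not give. At 5% v 25% loss, the 90-day contrast moves by roughly 2 to 3 points from a true 10, in a direction set by how the lost are coded, and chi-square rejects about 7% of the time under no difference. A t test on time would reject 22% to 25% of the time. With no loss, or equal 10% loss, the problem almost vanishes. The near-immunity of the 30-day result assumes that loss starts at day 14; earlier loss would affect it more. Mortality, PAD share, exponential survival and loss unrelated to prognosis are all assumptions.

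**What to change.** **Section 6, item 8 (Statistical method).**
- Define all-cause mortality at day 30 and at day 90.
- Analyse survival to day 90 by Kaplan-Meier curves, a log-rank test and a Cox hazard ratio with 95% CI, censoring at the date last known alive or day 90, whichever is earlier.
- Report the Kaplan-Meier 30-day and 90-day mortality differences with 95% CIs.
- Report the number lost or withdrawn by PAD group. Add a simple sensitivity analysis, for example counting the lost first as alive and then as dead.

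**Section 6, item 7 (The follow-up).** Record the date of each event and, at each contact, the date last known alive. Seek vital status at days 30 and 90 for every patient who has not withdrawn.

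The cost is SAP wording and two date fields on the follow-up form, plus the effort of tracing vital status; no extra visits or patients are needed. The date fields should be in place before follow-up ends, because a date last known alive is hard to recover later.

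### Only Student's t test is named for continuous variables, with no provision for unequal variances, although the PAD and non-PAD group sizes depend on an unknown prevalence

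*Combined protocol and SAP*

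**What the plan says.** The Statistical method item of section 6 (Methods and procedures) contains the whole analysis plan.

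- Sample size: "We plan to enroll 200 patients".
- Groups: "Patients will be grouped into patients with PAOD and patients without PAOD". The study method item defines the condition: "If ABI < 0.9, a diagnosis of PAD is made".
- What is compared: "clinical data, laboratory data, survival and other outcome data".
- Test for continuous variables: "Two-sample student's t tests will be used for the comparisons of continuous variables". Categorical variables go to the chi-square test.
- Threshold: "Difference is considered statistically significant if" P < 0.05, with sidedness not stated.
- Software: SPSS 17.0 and R, with no variance option specified.

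The plan does not mention equal or unequal variances, a variance check, Welch's test or a rank test. It gives no expected group sizes. Prevalence in this population is an objective in section 5: "To evaluate the prevalence of PAD among patients admitted to our intensive care units". The one prevalence figure, in the Background, is 48–30% and refers to hemodialysis patients screened at the same hospital.

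**The concern.** Student's test pools the two variances into one estimate. When the groups are of equal size this does no harm to the error rate. When they are not, the pooled estimate leans towards the larger group. The standard error is then too small if the smaller group is the more variable one, and too large if it is the less variable one. A larger total sample does not remove this, because the distortion depends on the allocation and on the ratio of the SDs.

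Nothing in the design keeps these groups equal: membership follows from a measurement made after enrollment. The comparisons at stake are those of continuous clinical and laboratory characteristics, such as the APACHE score and blood pressure. They deserve some care because the Statistical method item names no adjusted analysis. The unadjusted comparison of characteristics is therefore what a reader would use to judge how alike the groups were before attributing an outcome to PAD. A liberal test would report differences that are not there. A conservative one would miss real imbalances.

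**Working it through.** **Inputs from the documents:** N = 200; nominal level 0.05; grouping by ABI < 0.9; prevalence 48–30% in hemodialysis patients.

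**Assumptions:** two-sided testing; the pooled form of the test; normal data; PAD shares from 10% to 50%; r = SD(PAD)/SD(no PAD) from 0.5 to 2. The documents give no SDs and no prevalence for sepsis patients.

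**Formula.** With n1 and s1 for PAD, n2 and s2 for no PAD:

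- V_pooled = [((n1−1)s1² + (n2−1)s2²)/(n1+n2−2)] × (1/n1 + 1/n2)
- V_true = s1²/n1 + s2²/n2
- Actual two-sided error = 2 × (1 − Φ(1.96 × √(V_pooled/V_true)))

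**The plan's own figure.** With s1 = s2 the ratio V_pooled/V_true is 1, so the formula returns 2 × (1 − Φ(1.96)) = 5.0% at every split. The 5% level is reproduced when variances are equal.

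**Worked cases (s2 = 1):**

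- 96 v 104, r = 2: V_pooled = (483/198) × 0.02003 = 0.04887; V_true = 4/96 + 1/104 = 0.05128; √ratio = 0.976; error 5.6%.
- 96 v 104, r = 0.5: V_pooled = (126.75/198) × 0.02003 = 0.01282; V_true = 0.25/96 + 1/104 = 0.01222; √ratio = 1.024; error 4.5%.
- 60 v 140, r = 2: V_pooled = (375/198) × 0.02381 = 0.04509; V_true = 4/60 + 1/140 = 0.07381; √ratio = 0.782; error 12.6%.
- 60 v 140, r = 0.5: V_pooled = (153.75/198) × 0.02381 = 0.01849; V_true = 0.25/60 + 1/140 = 0.01131; √ratio = 1.279; error 1.2%.
- 40 v 160, r = 2: V_pooled = (315/198) × 0.03125 = 0.04972; V_true = 4/40 + 1/160 = 0.10625; √ratio = 0.684; error 18.0%.

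**Actual error of the pooled test at nominal 5%, by formula:**

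| PAD share (split) | r = 0.5 | r = 0.8 | r = 1.25 | r = 1.5 | r = 2 |
|---|---|---|---|---|---|
| 50% (100 v 100) | 5.0% | 5.0% | 5.0% | 5.0% | 5.0% |
| 48% (96 v 104) | 4.5% | 4.8% | 5.2% | 5.4% | 5.6% |
| 40% (80 v 120) | 2.7% | 4.1% | 6.1% | 7.0% | 8.3% |
| 30% (60 v 140) | 1.2% | 3.2% | 7.3% | 9.4% | 12.6% |
| 20% (40 v 160) | 0.4% | 2.5% | 8.6% | 12.2% | 18.0% |
| 10% (20 v 180) | 0.1% | 1.9% | 10.1% | 15.5% | 24.8% |

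**Check by simulation.** With 200,000 normal data sets per cell, the pooled test agrees with the formula to within about 0.15 percentage points. Allowing for simulation error, the range at 96 v 104 is about 4.4–5.7%, and the low end at 40 v 160 is about 0.5%.

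**The alternative.** In the same simulations Welch's test gives 4.9–5.1% in every cell. Its power cost was checked with equal SDs at a difference set for a nominal 80%. At 60 v 140 (0.432 SD) power is 79.4% for Welch and 79.7% for the pooled test. At 96 v 104 (0.397 SD) it is 79.7% for both.

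**The case against.** The strongest reply is that the documents show no actual error. They do not write pooled or equal variance. That is the usual meaning of Student's test, but the name is also used loosely. Of the two packages named, SPSS prints the unequal-variance result beside the pooled one and R uses Welch by default, so the analyst may end up with the safer test anyway. No SDs, distributions or group sizes are given. At the upper quoted prevalence the groups are nearly equal and the problem almost disappears. The named outcomes are mortality, infarction, stroke and amputation, which do not go to a t test, and no stated decision depends on the p-values for patient characteristics.

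Most of this stands and sets the weight of the point. It rules out three readings that a reader might be tempted by:

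- **That the 5% rate fails whenever spreads differ.** It does not: at 100 v 100 it stays at 5%, and at 96 v 104 it barely moves even with a twofold SD ratio.
- **That the groups are known to be unequal, or the PAD group known to be more variable.** Neither is documented, so neither the presence nor the direction of an error can be shown.
- **That skewed laboratory values call for a log scale.** The documents give no distributions, and the calculation used normal data. A log scale would change the comparison to geometric means, and choosing it variable by variable would add a data-dependent decision.

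The reply does not remove the gap itself. If another form of the test was intended, the text does not say so, and leaving the option open allows the choice to be made after both results are visible. Nor is 30% a worst case: any lower prevalence makes the distortion larger.

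**Conclusion.** The point holds in conditional form. The plan names only Student's t test and has no provision for unequal variances, while the allocation depends on an unknown prevalence. Within the one prevalence range in the documents, the consequence of a twofold SD ratio runs from negligible (about 4.4–5.7% at 96 v 104) to material (about 1.2–12.6% at 60 v 140). At an assumed 20% prevalence it reaches about 0.5–18%. These sizes rest on the pooled reading, two-sided tests, normal data, and assumed prevalence and SD ratios. They measure exposure, not a realised error.

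The weight is low. The point bears mainly on continuous clinical and laboratory characteristics. It does not show that the comparisons of mortality, stroke, infarction or amputation, or the prevalence estimate, are affected. It is worth raising because the remedy is almost free.

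**What to change.** In the Statistical method item of section 6, replace the words naming two-sample Student's t tests with: two-sample Welch (unequal-variance) t tests. No transformation clause is needed for this point.

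The cost is one phrase. Both named packages provide the test, the sample size and data collection are unchanged, and the loss of power with equal SDs is at most 0.3 percentage points in the two splits checked (79.7% − 79.4% at 60 v 140; none at 96 v 104). Fixing the choice in advance also settles which of the two results is to be reported.
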